**1/8/2022**

## Introduction and Review

With increasing demands of the patient regarding aesthetics and function, the need for implant supported reconstructions has substantially increased. Extensive research is being done to improve the success of implant therapy. Numerous changes in the alveolus that follow tooth loss, frequently compromises dental implant placement in a prosthetically ideal position. The natural remodelling processes of alveolar socket begin immediately after extraction and may result in up to 50 % resorption of the alveolar ridge within 3 months (**Deepika-Penmetsa, S. L et al., 2017**).

Dental implant has become an important treatment option for the treatment of partial and complete edentulism. High failure rates have been associated with implants placed in resorbed ridges with insufficient alveolar bone structure. Placement of implants in non-ideal positions as a result of bone deficiency may lead to the application of off-angle forces to the implant during function which significantly increases the force magnitude applied to the bone around the implant (**Aeh, A. et al., 2017**).

Several classification systems of alveolar ridge deformities have been proposed. Seibert introduced his widely used classification of ridge defects in 1983. In this classification, Class I defects represent buccolingual loss of tissue and normal apicocoronal ridge dimensions, Class II defects are those with apicocoronal loss of tissue and normal buccolingual ridge dimensions, while Class III defects represent a combination of both width and height deficiencies. In 1988, Cawood and Howell suggested an anatomic classification of the edentulous jaws for the preprosthetic surgery. It proposed six classes and detailed the changes that the edentulous alveolar process in anterior and posterior maxilla and mandible undergo after teeth extraction (the pattern of resorption). In 1989, Jensen proposed an implant-driven site classification by bone quality and quantity and proximity to vital structures. In 2002, Wang and Al-Shammari described a practical (therapeutically oriented) classification of alveolar ridge defects, that is, horizontal, vertical, and combination defects, proposing the edentulous ridge expansion approach (ridge-split) for the horizontal and combination defects of the alveolar Ridge. (**Cawood, J. I. et al., 1988**) (**Jensen O. 1989**) (**Wang, H. L. et al., 2002**)

Bone regeneration and reconstruction **in** patients with severely atrophic ridges have been always controversial. Although several techniques can be used, it can be difficult to find an appropriate technique that provides bone with properties similar to those of the recipient site (**Pourdanesh, F. et al., 2017**).

Various alveolar ridge augmentation procedures are available to gain enough bone volume and apply the ideal treatment plan afterwards. Guided bone regeneration, ridge splitting, distraction osteogenesis and autogenous block bone grafting are main techniques which have successful outcomes in reconstruction of bone defects. It's difficult to demonstrate that one augmentation procedure offers better outcomes than another. Studies documenting augmentation techniques seem to be comparable and state favorable results for each procedure. (**Aytekin, M. et al., 2020**)

A number of grafting materials are available. The use of autogenous bone grafts for ridge repair has been considered as the gold standard for obvious biological reasons because of its inherent osteogenic, osteoinductive, and osteoconductive properties. However, the surgical morbidity associated with graft procurement procedures has triggered countless attempts to avoid a second surgical site for graft procurement by using allografts, xenografts, or synthetic material to replace the lost alveolar bone (**Troeltzsch, M. et al., 2016**) (**Patel, A. et al., 2019**).

Allografts are transferred from an individual to another within the same species. Since there is no need for a secondary surgical site to obtain allografts, reduced morbidity is one of the advantages brought by use of this graft. Unlimited source is another advantage over autografts. Although allografts have no osteogenic properties, they stimulate bone growth via osteoconduction and incorporation of osteoinductive growth factors. There are strict sterilization and decontamination protocols regarding these materials due to the risk of disease transmission and host immune response. Donors are carefully evaluated and graft materials are gradually processed to avoid any risks. Some studies reported that certain allografts are less osteoinductive than others because of the sterilization protocols and the variability of their content (**Aytekin, M. et al., 2020**).

One of the most popular techniques is guided bone regeneration (GBR), which entails placing a membrane over the defect to create a secluded space into which osteogenic cells can migrate and remain undisturbed over the exposed part of the implant. Guided bone regeneration (GBR) is frequently used in combination with the installment of titanium implants. The application of a membrane to debar non-osteogenic tissues from interfering with bone regeneration is a key principle of GBR (**Elgali I et al., 2017**) (**Vijayalakshmi R et al., 2012**).

The tenting technique, which originated from the principles of guided bone regeneration, involves raising the periosteum like a tent to allow osteoblasts to migrate into the gap to start osteogenesis. The gap that is made is then filled with osteoconductive or osteoinductive materials, and in some cases, both. The migration of epithelial cells can be prevented by the application of a barrier-like collagen membrane or other component. The technique is divided into three categories that depend on the method that is used to keep the periosteum up. the first of which was the tent-pole technique. The two other modifications, cortical autogenous tenting, and screw tenting, are usually used for smaller oral defects. Studies have shown that they can all be used to augment bone effectively (**Khojasteh, A. et al., 2012**) (**Takata, T. et al., 2001**) (**Marx, R. E et al., 2002**).

To avoid shrinkage resulting from pressure after flap closure, several space maintenance modalities were used to facilitate reconstruct ridge formation such as tenting screws, titanium (Ti) meshes, and Ti-reinforced polytetrafluoroethylene (PTFE) membranes. Nonresorbable membranes have a high risk of exposure, necessitating removal in the re-entry stage. Resorbable membranes have shown better biocompatibility and support of underneath bone growth. However, their lack of stiffness can lead to decreased bone volume gain. Therefore, the tent-pole technique, which combines resorbable collagen membrane and tenting screws, represents an effective approach, offering easy manipulation and low complication rates (**Doan, Tu et al., 2020**).

## Aim of the study

**-First aim:** Evaluate the effectiveness of screw tent technique in horizontal ridge augmentation

**-Second aim:** Compare the effect of using single screw versus double screws on obtaining maximum bone gain.

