## Pre-surgical phase

- At the initial visit, each patient will receive a diagnostic work-up that included a full periodontal examination, standardized periapical radiographs and diagnostic study casts.
- Horizontal ridge width will be measured with a bone caliper to the nearest millimeter at the midridge crestal level and then 5 mm apically. Stent will be used for the standardization of the measurements.
- A preoperative cone-beam computed tomography (CBCT) will be performed for each patient who met the inclusion criteria before the surgery to determine bone height and width and to evaluate the underlying bone condition.
- These clinical and radiographic measurements will be repeated at reentry after 6 months of healing.

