### **Group A:**

: 8 patients indicated for lateral ridge augmentation in premolar-molar area (class I Seibert's classification) will be candidates to screw tent technique using single screw at crest position

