### **Group B:**

8 patients indicated for lateral ridge augmentation in premolar-molar area (class I Seibert's classification) will be candidates to screw tent technique using double screws, one at a crestal position and the other one 5 mm apical to the first one.

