## **Surgical Phase**

- All patients will receive prophylactic antibiotic (1 gm. Amoxicillin-clavulanate, Augmentin ®, GlaxoSmithKline, UK) one hour preoperatively and then every twelve hours for four days and will be instructed to rinse with 0.12% Chlorhexidine (Orovex ®, MACRO, Egypt) for one minute prior to surgery and twice daily for 2 weeks postoperatively.
- All procedures will be performed under local anesthesia utilizing articaine hydrochloride 4% with 1:100000 epinephrine (Septanest®, Septodont, USA).
- Sulcular incisions around teeth with mesial and distal vertical releasing incisions. A full thickness flap will be reflected on the buccal, and a full thickness flap will be reflected on the lingual/palatal to expose the residual alveolar ridge.
- Multiple cortical perforations will be performed with a 1/2 round bur to increase angiogenesis and supply of growth factors in all defect areas.
- In group A: single titanium bone screw will be placed in a crestal position to aid in graft stability. In group B: double titanium bone screws will be placed, one at a crestal position and the other one will be placed 5mm apical to the first one.
- In both groups the defect will be filled with allograft, the graft will be extended at least 10 to 12 mm in the apicocoronal direction.
- The grafted site will be covered with Bovine pericardium membrane
- Tension-free primary flap closure will be achieved and sutured using a 5-0 Polypropylene suture.
- 6 months later at the reentry, the bone screws will be removed and dental implant will be placed at the augmented site.

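### Does the first aim need an untented comparison arm, or rewording, because every patient receives the screw, graft and membrane together?

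*Protocol*

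**What the plan says.** The protocol's Aim of the study lists two aims. The first is to "Evaluate the effectiveness of screw tent technique in horizontal ridge augmentation". The second is a comparison of single with double screws for bone gain. Neither is labelled primary.

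The two groups of 8 differ only in the number of screws. Group A has "screw tent technique using single screw at crest position" and Group B has "screw tent technique using double screws". The Surgical Phase section gives the remaining components to everyone: "In both groups the defect will be filled with allograft", "The grafted site will be covered with Bovine pericardium membrane", and cortical perforations are made in all defect areas.

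The Pre-surgical phase section sets out caliper ridge width and CBCT at baseline and adds: "These clinical and radiographic measurements will be repeated at reentry after 6 months of healing". Clinical assessment and Radiographic evaluation confirm the 6-month width measurements.

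The Introduction and Review explains why screws are used. Of resorbable membranes it says that "their lack of stiffness can lead to decreased bone volume gain", and it then commends a technique that "combines resorbable collagen membrane and tenting screws".

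**The concern.** Effectiveness usually means effectiveness against something. The Introduction supplies a natural candidate: a resorbable membrane is too soft to hold space, and screws make good that weakness. A reader who goes from that argument to the first aim may expect the trial to show that tenting improves on graft plus membrane.

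The design cannot show this. Nobody is treated without a screw, so any 6-month gain belongs to the whole procedure. The only randomised contrast concerns the second screw, which informs the second aim. If the gain were reported as the benefit of tenting over grafting alone, the claim would have no support in the data, and a larger trial with the same two arms would not supply it. The uncontrolled question is also listed ahead of the randomised one.

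**Working it through.** The protocol gives no effect size, SD, alpha or power, so it has no figure to reproduce. The check is whether the design can estimate what is asked of it.

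**Inputs.** 16 patients, 8 per group (Patient selection; Randomization). Components by group (Group A; Group B; Surgical Phase):

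| | Graft, membrane, perforations | First screw | Second screw |
|---|---|---|---|
| Group A | yes | yes | no |
| Group B | yes | yes | yes |

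**Step 1: the effect of tenting on its own.** Let c be the mean gain from graft, membrane and perforations, s1 the contribution of the first screw and s2 that of the second, taken as additive. Then

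- mean gain in A = c + s1
- mean gain in B = c + s1 + s2

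Subtraction gives s2. Only the sum c + s1 is otherwise available. The 16 × 3 design matrix has rows (1,1,0) and (1,1,1), so its first two columns are identical and its rank is 2 of 3. An added arm with row (1,0,0) would bring the rank to 3.

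As an illustration with assumed means of 3.0 mm in A and 3.5 mm in B (the protocol gives none), the splits (c, s1, s2) = (3.0, 0, 0.5), (1.5, 1.5, 0.5) and (0, 3.0, 0.5) fit equally well. The design fact behind the concern is therefore correct.

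**Step 2: what the aims ask for.** The three-way split above is not in the protocol. The aims imply two quantities: the gain under the technique, g = c + s1 with one screw, and the increment from a second screw, s2. Then

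- mean gain in A = g
- mean gain in B = g + s2

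The rows are (1,0) and (1,1), and the rank is 2 of 2. Both quantities are estimable.

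**Step 3: precision, in SD units because no SD is given.** The half-width of a 95% interval for a mean change is t(0.975, n−1)/√n:

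- all 16 patients: 2.131/4 = 0.53 SD
- one group of 8: 2.365/2.828 = 0.84 SD

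For s2, at an assumed two-sided 5% level and 80% power, the detectable difference is (1.960 + 0.842) × √(2/8) = 1.40 SD by the normal approximation, or 1.51 SD by the t-test. The trial is small, but that is separate from whether the first aim can be answered.

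**Step 4: which reading the text supports.**

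- The verbs differ: the first aim evaluates, the second compares. The only comparison announced is the one randomised.
- The Introduction describes tenting as lifting the periosteum, filling the space beneath with graft material and, where used, adding a barrier. On that description the graft and membrane are part of the technique, and the whole procedure is the object of the first aim.
- The stiffness remark is background on why the method was chosen. The sentence that follows it is about the tent-pole technique, which the Introduction lists separately from screw tenting, although it does mention tenting screws.
- The Introduction also says that superiority of one augmentation procedure over another is hard to show, which points away from a hidden superiority claim.
- Ridge width has the baseline and 6-month measurements that a within-patient answer needs.

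**The case for a change.** The strongest case for a change is that it would be cheap. The aim, the arms and the shared components are fixed in the protocol, so no analysis plan can recover the missing contrast. A sentence limiting the first aim to descriptive change would guard against over-claiming, and naming the randomised comparison as primary would put the stronger evidence first. Patients and procedures would be untouched.

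Much of this stands. The contrast is unrecoverable, the word effectiveness is loose without a comparator, and a paper from this trial should not credit the gain to the screws.

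It falls short of a reason to amend the plan. The harm depends on a future reader taking background text as a hypothesis; the protocol itself does not make the claim. Naming a primary comparison and specifying a confidence interval are commonly left to a statistical analysis plan, which is not at hand here. The order of two listed aims is a matter of preference and alters no estimate. A no-screw arm would make a different trial, with a question that this protocol does not pose.

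**Conclusion.** No change follows. The contribution of tenting over graft plus membrane is not identifiable, with 0 of 16 patients untented, but it is not a stated objective. The first aim can be answered as the mean within-patient change in ridge width after the combined procedure, to about ±0.53 SD over all patients or ±0.84 SD within a group. The second aim is answered by the randomised comparison. An analyst following the protocol would produce both without further instruction, and extra wording would alter neither.

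This rests on two things. The first is reading the technique as the whole procedure, which the Introduction supports. The second is confining the before-after answer to ridge width: keratinized mucosa and bone density are named explicitly only at 6 months. Since the Introduction describes bone loss as the course after extraction, a gain in width could fairly be credited to the procedure as a whole, though not to the screws alone.

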# Patients and Methods

## Patient selection

this study will be conducted on 16 patients indicated for horizontal ridge augmentation in premolar and molar area. After approval from the ethical committee, the entire patients will be recruited from the outpatients' clinic of the Oral Medicine, Oral Diagnosis, and Periodontology Department Faculty of Dentistry, Minia University.

### Inclusion criteria:

1. Selected patients of both genders are 20-55 years old.
2. Patients are systemically healthy based on questionnaire dental modification of Cornell index (**Bolender, C. L. et al., 1969**).
3. Gingival health according to the new classification system (**Caton, J. G. et al., 2018**).
4. The recipient site of the augmentation is free from any pathological conditions.
5. At least 1 tooth area with a ridge defect and planned to receive a dental implant. The site must be bordered by at least 1 tooth.
6. Class I ridge defect according to Seibert's classification.
7. Adequate interocclusal space to accommodate the available restorative components.

### Exclusion criteria:

1. Pregnant female.
2. Parafunctional habits such as bruxism and clenching.
3. Smokers.

## Ethical regulation and Informed consents

All patients will undergo a delayed implant placement and the complete treatment plan will be explained to all patients including detailed steps, risks, and expected results. Verbal and written informed consent will be obtained from all patients before the commencement of the study. All steps will be examined and approved by the appropriate ethics committee and have therefore been performed following the ethical standards laid down in the Declaration of Helsinki and the research ethics committee of the Faculty of Dentistry, Minia University.

## Pre-surgical phase

- At the initial visit, each patient will receive a diagnostic work-up that included a full periodontal examination, standardized periapical radiographs and diagnostic study casts.
- Horizontal ridge width will be measured with a bone caliper to the nearest millimeter at the midridge crestal level and then 5 mm apically. Stent will be used for the standardization of the measurements.
- A preoperative cone-beam computed tomography (CBCT) will be performed for each patient who met the inclusion criteria before the surgery to determine bone height and width and to evaluate the underlying bone condition.
- These clinical and radiographic measurements will be repeated at reentry after 6 months of healing.

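### Does reading ridge width 5 mm apical to the crest, nominally where only group B has a screw, bias the single-versus-double-screw comparison?

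*Protocol*

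**What the plan says.** Only the Protocol is at hand. The relevant statements are these.

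- **Where width is read.** Pre-surgical phase: "Horizontal ridge width will be measured with a bone caliper to the nearest millimeter at the midridge crestal level and then 5 mm apically". Clinical assessment repeats both levels at six months and requires the stent used at baseline.
- **When it is read again.** Pre-surgical phase: "These clinical and radiographic measurements will be repeated at reentry after 6 months of healing".
- **Hardware.** Group A receives the "screw tent technique using single screw at crest position". Group B receives two screws, "one at a crestal position and the other one 5 mm apical to the first one". Surgical Phase repeats this ("the other one will be placed 5mm apical to the first one") and states that the screws are titanium.
- **Removal.** Surgical Phase: "6 months later at the reentry, the bone screws will be removed and dental implant will be placed at the augmented site".
- **Imaging.** Radiographic evaluation plans six-month cone-beam CT (CBCT) for ridge width and bone density. It gives no measuring level and no timing relative to screw removal.
- **Purpose.** The second aim is to "Compare the effect of using single screw versus double screws on obtaining maximum bone gain". Density appears in neither aim.

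**The concern.** The second caliper level and group B's second screw are both described as 5 mm apical to something crestal. Read at face value, they coincide, and group A has no screw there. The second screw is also the only planned difference between the arms. If the six-month reading were taken with the screws still in and a caliper tip resting on metal, the error would arise in group B and not in group A. Randomisation would not balance it, because it would follow the treatment itself. Subtracting baseline would not remove it, because baseline is read before any screw is placed. The shared stent fixes where the reading is taken, not whether metal is there.

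With 8 patients per arm and readings to the nearest millimetre, a systematic shift in one arm could be mistaken for a difference in bone gain, which is what the second aim compares. CBCT width or density near that level might be affected as well if the scan preceded removal.

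**Working it through.** The Protocol gives no figure to reproduce here: no effect size, standard deviation or error bound for the reading. The check therefore asks when the arms could differ, and whether that amounts to a reading error.

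**Inputs.** Levels are counted apically from the crestal reading level.
- Readings at 0 and 5 mm (Pre-surgical phase, Clinical assessment).
- Crestal screw at depth *d* in both arms; second screw at *d* + 5 in group B only (Group A, Group B, Surgical Phase).
- *d* is not given; assumed 0 to 3 mm.
- *m*, the mesiodistal distance of the screws from the stent line, is not given; assumed 0 or 3 mm, equal for both screws and both arms.

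**Distance from the 5 mm reading to the nearest screw axis.**
- Group A: A = √((5 − d)² + m²)
- Group B: B = min(A, √(d² + m²))

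| d (mm) | A, m = 0 | B, m = 0 | Gap | A, m = 3 | B, m = 3 | Gap |
|---|---|---|---|---|---|---|
| 0 | 5 | 0 | 5 | 5.83 | 3.00 | 2.83 |
| 1 | 4 | 1 | 3 | 5.00 | 3.16 | 1.84 |
| 2 | 3 | 2 | 1 | 4.24 | 3.61 | 0.64 |
| 2.5 | 2.5 | 2.5 | 0 | 3.91 | 3.91 | 0 |
| 3 | 2 | 2 | 0 | 3.61 | 3.61 | 0 |

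The gap is positive only when d < 5 − d, that is, d < 2.5 mm. At the crestal reading both arms are √(d² + m²) from a screw, so the gap is 0.

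**From distance to reading error.** A caliper reading changes only if a tip meets metal. Let *r* be the screw-head radius plus half the tip width (not given). Group B is affected and group A is not when √(d² + m²) < r ≤ √((5 − d)² + m²). At m = 3 this needs r above 3 mm even for d = 0; with a smaller r the tabulated gaps have no effect on the caliper. At m = 0 and d = 2 it needs r above 2 mm. Overlap is thus confined to small *d* and small *m* together, and only with the screws in place.

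**If a shift did occur.** Suppose, purely as an assumption, that k of the 8 group B readings moved by 1 mm. The group B mean moves by k/8: 0.25, 0.5 or 1.0 mm for k = 2, 4 or 8. With no true difference, a two-sided 5% t test with 8 per arm and an assumed SD of 1.0 mm would reject in about 7.5%, 15% and 46% of trials. Across assumed SDs of 0.75 to 1.5 mm the range is about 6% to 70%. These figures show sensitivity to an invented shift. Neither the shift nor the SD is in the Protocol, so they are no evidence that it happens.

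**Comparing the sections.** Pre-surgical phase and Surgical Phase place measurement, screw removal and implant placement at one reentry, and Clinical assessment repeats the reading there. These statements are consistent with each other. Reading before removal and reading after it both satisfy them.

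Order is also not the whole matter. After removal, group B has a screw hole at the nominal 5 mm site and group A does not. In either order, what protects the reading is that the tips rest on bone. The Protocol already points that way by naming ridge width as the quantity and a bone caliper as the instrument.

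**The case for a change.** The strongest argument for a change is that the text permits either order, and permits it to vary between patients. Once the screws are out and the implant is in, the order cannot be recovered by any analysis. This is measurement procedure, which this Protocol sets out itself, so it cannot be passed to an analysis plan. Writing down one order for both arms would cost a sentence and would need no extra patients or scans.

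Most of that is true: the order is unstated, and stating it would be cheap. What it does not show is that the plan as written produces a biased reading. Bias needs the screws still in place, a crestal screw close to the crestal reading level, a stent line running over the second screw, and an operator who accepts a reading over metal. The text states none of these, and the last sits badly with measuring ridge width by bone caliper.

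The CBCT part is weaker. No level is fixed for CBCT, so the 5 mm coincidence does not carry over and width can be read beside the screw. The inclusion criterion "At least 1 tooth area with a ridge defect and planned to receive a dental implant" means that a site may be small and a metal-free section may not always be available. That is a limit of the site, which a reading rule would not remove. Density serves neither aim.

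**Conclusion.** The factual observation is right: the 5 mm caliper level is nominally that of group B's second screw, and the six-month readings are not ordered against screw removal. It does not call for a change. Nothing in the Protocol is misstated or contradictory here. The missing item is a step order within one visit, which those taking the measurements can fill sensibly by keeping the caliper on bone, clear of any screw or screw hole, in the same way in both arms and before the implant goes in.

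The size and direction of any error are unknown. The only derivable quantity, a difference between arms of 0 to 5 mm in distance to the nearest screw axis, rests on assumed values of *d* and *m* and measures proximity, not error. The crestal caliper reading, where both arms have a screw, and CBCT width read beside the screw give a partial check. The conclusion assumes that the operator measures bone, as the Protocol's wording implies; a practice of reading over screw heads would make it a real concern, but nothing in the document suggests one.
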